## REVISION HISTORY

Revision #	Version Date	Summary of Changes	Consent Change?
2	June 2, 2021	Revision of protocol to exclude the AIM2DOSE intervention and add LOAN2DOSE. Protocol Title Change.	YES
3	September 22, 2021	Update to the number of participants enrolled Update to pg. 13 Study timelines	Yes
4	January 26, 2022	Changed the word 'Dexcom' to 'CGM' on pages 10,11, 13, & 15	Yes
5	May 12, 2022	Update the use of a recruitment flyer and use of POC a1c if research a1c not received	No
5	Feb 23, 2023	Updated bolus scoring protocol, the dinner window is changed to end at 2200 H.	No
6	April 5, 2023	Updated the use of email to invite potential subjects to participate.	No
7	July 19, 2023	Remove that parents can participate in study focus group even if their child does not participate (page 12). Parents may participate in focus group if their child is enrolled in the study. Removed study AIM 4 (page 6). 1 sentence added to clarify insulin delivery system deliver tracking (page 13). Remove artificial intelligence aspect of focus group consent.	yes
8	Dec 26, 2023	Correct conflicting information in Section 25.0 about Telephone Consent process.  Update policy reference from 10.05 to "IRB Permission/Assent/Consent Policy" in Section 25.0 and 26.0.	No

## 1.0 Study Summary

Study Title	HCT Cash-Only IN centive to promote mealtime insulin DOSE Engagement (HCT COIN2DOSE): a pilot trial
Study Design	Pilot randomized controlled trial
Primary Objective	To determine the impact of HCTCOIN2DOSE and LOAN2DOSE compared to control on the trajectory of glycemic control and treatment engagement among adolescences age 12-17 years who are at risk for a near-term rise in A1C.
Secondary Objective(s)	To determine both the feasibility and usability of HCTCOIN2DOSE and LOAN2DOSE intervention compared to control in adolescents age 12-17 years who are at risk for a significant near-term rise in A1C.
Research Intervention(s)/ Investigational Agent(s)	HCT COIN2DOSE: Utilization of immediate financial incentives to promote mealtime insulin dose delivery, with weekly bonuses for sustained meal dosing behavior LOAN2DOSE: Utilization of loss aversion approach to promote mealtime insulin dose delivery. Participants will start with a virtual bank balance and will have money deducted from the balance when mealtime insulin doses are missed. Additional amounts will be deducted when sustained meal dosing goals are not met.
IND/IDE #	NA
Study Population	Individuals identified by artificial intelligence who are predicted to experience a rise in A1C of greater than or equal to 0.3% in the next 70-110 days using a validated predictive algorithm created via advanced machine learning (random forest) and natural language processing. Individuals must have had the diagnosis of T1D for 6 months and be 12-17.99 years old. Parents of children who meet inclusion criteria may choose to participate in the focus group
Sample Size	A minimum of 36 and a maximum of 72 youth randomized in a 1:1:1 ratio to either the treatment or usual care (control).  Participants and their parents may choose to participate in the focus group. Parents may enroll in the focus group if their child is enrolled in the study. Our aim will be to enroll 5 to 30 parents.
Study Duration for Individual Participants	26 weeks (11-13 weeks intervention and 11-13 weeks observation Participants and/or their parents may choose to participate in a focus group at the end of the study (week 26).

Study Specific Abbreviations/ Definitions	T1D = Type 1 diabetes COIN2DOSE = Behavioral Economic Incentives to promote insulin Dose Engagement in Adolescents with Type 1 Diabetes LOAN2DOSE = Behavioral Economic concept that uses an economic loss aversion approach to promote insulin dose engagement in adolescents with Type 1 Diabetes CGM = continuous glucose monitoring AI = artificial intelligence SOC = Standard Care Diabetes Clinic Visit Twilio= cloud-based communication platform that enables clinic staff to send secure SMS text messages to participants
--	--

## 2.0 Objectives

### 2.1 Primary Objectives

The long-term goal is to develop effective ways to improve glycemic control in youth with T1D. To that end, we propose to specifically evaluate the effectiveness, feasibility, and usability of two new interventions in diabetes care: an economic incentive (COIN2DOSE) and an approach that uses an economic loss aversion (LOAN2DOSE) to promote patient engagement with mealtime insulin dosing behavior. If initially efficacious, our results will serve as the basis for an R01 submission(s) to conduct a fully powered efficacy trial of COIN2DOSE and LOAN2DOSE. This study is significant as omission of mealtime boluses is one of the common reasons for suboptimal diabetes control in youth. This project is highly innovative because it will: 1) target youth who are predicted by artificial intelligence to experience a worsening in glycemic control, 2) use an economic incentive intervention to improve mealtime insulin dosing behavior and 3) use an economic loss aversion to improve mealtime insulin dosing behavior.

### 2.2 Hypotheses

**Aim 1: To determine the impact of COIN2DOSE and LOAN2DOSE as compared to control on the trajectory of glycemic control and treatment engagement among adolescents age 12-17 years who are at risk for a near-term rise in A1C.**

Hypothesis 1: Use of COIN2DOSE will result in a lower rise in A1C compared to the controls.

Hypothesis 2: Use of COIN2DOSE will improve engagement as measured by mealtime insulin BOLUS score compared to controls.

Hypothesis 3: Use of COIN2DOSE will yield sustained improvements in A1C trajectory for 12 weeks after the intervention.

Hypothesis 4: Use of COIN2DOSE will yield sustained improvements in BOLUS score for 12 weeks after the intervention.

Hypothesis 5: Use of LOAN2DOSE will result in a lower rise in A1C compared to the controls.

Hypothesis 6: Use of LOAN2DOSE will improve engagement as measured by mealtime insulin BOLUS score compared to controls.

Hypothesis 7: Use of LOAN2DOSE will yield sustained improvements in A1C trajectory for 12 weeks after the intervention.

Hypothesis 8: Use of LOAN2DOSE will yield sustained improvements in BOLUS score for 12 weeks after the intervention.

**Aim 2: To determine the feasibility of COIN2DOSE and LOAN2DOSE interventions in adolescents age 12-17 years who are at risk for a significant near-term rise in A1C.**

Hypothesis 9: The COIN2DOSE intervention will be feasible as determined by 1)  $\geq 75\%$  of participants in the intervention group will complete all study procedures for the duration of the intervention and post-intervention study periods, 2)  $\geq 75\%$  of parents will endorse the feasibility of providing an equivalent economic incentive plan, and 3) no decrease in quality of life at visit 2 compared to baseline (visit 1).

Hypothesis 10: The LOAN2DOSE intervention will be feasible as determined by 1)  $\geq 75\%$  of participants in the intervention group will complete all study procedures for the duration of the intervention and post-intervention study periods, 2)  $\geq 75\%$  of parents will endorse the feasibility of providing an equivalent economic loss aversion plan, and 3) no decrease in quality of life at visit 2 compared to baseline (visit 1).

**Aim 3: To determine user satisfaction with the COIN2DOSE and LOAN2DOSE intervention in adolescents age 12-17 years who are at risk for a significant near-term rise in A1C.**

Hypothesis 11: COIN2DOSE will be usable as determined by using the Diabetes Treatment Satisfaction Questionnaire (change version).

[figure not shown]
Hypothesis 12: LOAN2DOSE will be usable as determined by using the Diabetes Treatment Satisfaction Questionnaire (change version).

## **3.0 Background**

### **3.1 Background**

Individuals with T1D can have a tremendous impact on their own health outcomes if they follow their T1D treatment regimen (2) (3) (4). Unfortunately, many adolescents do not adhere to their treatment and experience increased risk for both immediate medical emergencies, long-term T1D-related complications, and mortality (3) (5). Diabetic ketoacidosis (DKA) occurs at a rate of 4.81/100 patient-years in individuals with established T1D and at a rate of 15.83/100 patient years in youth with an A1C  $>9\%$  (6). Adolescents who have poorly controlled T1D are much more likely to develop DKA (3)

(7). While health care professionals can offer guidance and recommendations, it is clear that traditional clinical interactions are not sufficient to promote optimal self-care and adherence for many adolescents (8) with the majority not reaching A1C targets (3). In fact, adolescents with T1D exhibit significant deterioration in glycemic control (aka rising A1C) from age 8 to 18 (9), as shown below.

A number of behavioral interventions have demonstrated utility in improving adherence behaviors in youth with T1D. Improved adherence behaviors are associated with better glycemic control and short and long-term health outcomes (3). On the other hand, lack of adherence can have serious consequences both acutely (DKA or severe hypoglycemic events) and long-term (retinopathy, neuropathy, nephropathy, and cardiovascular disease) (3). Missed mealtime boluses can have devastating metabolic consequences (16).

Adolescence is a particularly challenging time for individuals with T1D, with average A1C values that are 5% higher than during other periods of childhood and 14% higher than adults (22) (2). Glycemic control worsens from early childhood through age 16-18 (23). It is critically important to develop interventions to prevent deterioration in glycemic control. High glycemic variability is also associated with increased risk of long-term diabetes complications, such as microalbuminuria (24). Lack of adherence to diabetes treatment plans is one of the main causes of sub-optimal glycemic control (3) (25) (7). A significant part of this non-adherence is omission of insulin for ingested carbohydrates at snacks and meals, both by missing boluses entirely and by inaccurate carbohydrate counting (26) (16) (27) (28) (29). Studies have shown significant underestimation of carbohydrate content in meals of up to 20% (26). Furthermore, greater than 33% of adolescents fail to give insulin for >15% of their meals and snacks (16). Adolescents, on average, miss boluses for meals two times per week (28). In one study, youth who omitted insulin at least one time per week had an A1C of 8.8-9.5%, while those who consistently took meal-time insulin had a significantly lower A1C of 7.8-8.0% (28) (30). This is of great significance as poor glycemic control increases risk of both acute and chronic diabetes related complications (31). Meal bolus alarms on insulin pumps, which alarm at a preset time, lead to transient, modest changes in dosing behavior (32). “Lost focus” has been identified as a significant reason for missed meal-time boluses in adolescents (33). Exactly how to effectively maximize engagement with mealtime insulin dosing behavior among adolescents with T1D represents a critical gap in knowledge.

### 3.2 Rationale

There is an urgent need for a sustainable method that improves patient engagement with delivering mealtime insulin boluses. Improved engagement with mealtime boluses will lead to better glycemic control and will ultimately help reduce the risk of acute and chronic diabetes related complications.

Recent evidence suggests that financial incentives can successfully increase adherence to blood glucose monitoring among adolescents and young adults with type 1 diabetes with moderate to large treatment effect size. Specifically, one study of 10 adolescents evaluated a financial incentive program that delivered \$0.10 per fingerstick blood glucose test, with bonus incentives for  $\geq 4$  tests per day and a maximum achievable incentive of \$251.40 over 12 weeks. The authors found that SMBG increased from  $1.8 \pm 1.0$  to  $4.9 \pm 1.0$  tests per day ( $P < 0.001$ ) with 90% completing four or more tests per day; that mean A1C fell from  $9.3 \pm 0.9\%$  to  $8.4 \pm 1.5\%$  ( $P = 0.05$ ); and that adolescents and parents reported high satisfaction with procedures. In another study, 90 adolescents and young adults demonstrated that a \$60 monthly incentive opportunity significantly increased adherence to glucose monitoring goals in the 90-day incentive period (50.0% vs 18.9%; adjusted difference, 27.2%; 95% CI, 9.5% to 45.0%;  $P = .003$ ). The effect was not sustained during the post-interventional 90-day observation period (15.3% vs 8.7%; adjusted difference, 3.9%; 95% CI, -2.0% to 9.9%;  $P = .20$ ), and A1C did not improve. The evidence to date suggests that it is feasible to increase adherence behaviors among adolescents and young adults with type 1 diabetes. It is unclear whether targeting blood glucose monitoring behaviors is always associated with an improvement in A1C. Whether financial incentives produce a sustained improvement in adherence is also an open question. These methods have not been applied to mealtime insulin dosing behaviors, so whether financial incentives improve adherence to mealtime insulin dosing among adolescents and young adults is also unknown.

There is a strong rationale for targeting adherence to mealtime insulin dosing for improvement. Prior observational research suggests a 1.5% decrease in A1C levels for every one-bolus increase in daily mealtime doses, supporting our premise that increasing mealtime insulin use might help youth who are at risk of increasing A1C(1).

The objective of the present study is to obtain pilot feasibility data to 1) determine whether COIN2DOSE and/or LOAN2DOSE show a preliminary trend for improvement in the outcomes of interest, 2) perform power calculations that will inform the design of a definitive trial(s) and 3) establish feasibility of the interventions and study procedures to inform the design of a definitive trial(s).

## 4.0 Study Endpoints

### Outcome Measures

Primary outcome:

- 1) Change in A1C ( $\Delta A1C_{90\text{-day}}$ ) from baseline visit (visit 1) to 90-day visit (visit 2).

## Secondary outcomes:

- 1) Change in A1C ( $\Delta A1C_{180\text{-day}}$ ) from baseline visit (visit 1) to 180-day visit (visit 3).
- 2) Change in percent time in range 70-180 mg/dL (%TIR70-180) from baseline visit (visit 1) to 90-day visit (visit 2) and to 180-day visit (visit 3).
- 3) Change in percent time hyperglycemic ( $>180$  mg/dL; %Hyper>180) from baseline visit (visit 1) to 90-day visit (visit 2) and to 180-day visit (visit 3).
- 4) Change in percent Time hypoglycemic ( $<70$  mg/dL; %Hypo<70) from baseline visit (visit 1) to 90-day visit (visit 2) and to 180-day visit (visit 3).
- 5) Change in percent Time severely hypoglycemic ( $<54$  mg/dL) (%Hypo<54) from baseline visit (visit 1) to 90-day visit (visit 2) and to 180-day visit (visit 3).
- 6) Change in mealtime insulin BOLUS score (BOLUS) from baseline visit (visit 1) to 90-day visit (visit 2) and to 180-day visit (visit 3).
- 7) For COIN2DOSE treatment group, proportion of participants who complete  $>90\%$  of study procedures throughout the intervention and post-intervention study procedures.
- 8) For COIN2DOSE treatment group, proportion of parents who endorse the feasibility of providing an economic incentive equivalent to that used in the intervention.
- 9) For COIN2DOSE treatment group,  $>75\%$  of participants will exhibit a score of  $>80\%$  total possible points on Diabetes Treatment Satisfaction Questionnaire (teen version)
- 10) Change in trust in provider from baseline visit (visit 1) to 90-day visit (visit 2) and to 180-day visit (visit 3).
- 11) For LOAN2DOSE treatment group, proportion of participants who complete  $>90\%$  of study procedures throughout the intervention and post-intervention study procedures.
- 12) For LOAN2DOSE treatment group, proportion of parents who endorse the feasibility of providing an economic incentive equivalent to that used in the intervention.
- 13) For LOAN2DOSE treatment group,  $>75\%$  of participants will exhibit a score of  $>80\%$  total possible points on Diabetes Treatment Satisfaction Questionnaire (teen version)
- 14) Change in perceived involvement in care from baseline visit (visit 1) to 90-day visit (visit 2) and to 180-day visit (visit 3).
- 15) Change in health-related empowerment from baseline visit (visit 1) to 90-day visit (visit 2) and to 180-day visit (visit 3).

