## 13.0 Local Number of Subjects

Target sample size is 36 adolescents. The maximum number of subjects enrolled will be 72.

Parents or legal guardians of youth eligible for inclusion in the study may choose to participate in a focus group. We may enroll up to 30 parents or legal guardians.

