### *20.2 Power analysis*

To evaluate the primary outcome: glycemic control (measures as predicted trajectory of A1C over 90 days), a multivariable regression model will be developed that accounts for seven independent variables: two primary – adherence and quality of life – and an additional five covariates: participant age, sex, insurance status, intervention/control group status, and time (52). Using an F-test and significant level (alpha) of 0.025, a sample of 20 T1D patients per treatment arm would achieve 74% power to detect an effect size of 0.35 (53). Findings from this pilot study will be used as estimates in planning future studies including recruitment of enough patients to achieve a power of greater than or equal to 80% to evaluate glycemic control (54).

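### The single one-sided significance rule names no direction and exempts no outcome, which suits the two hypoglycaemia outcomes badly

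*Protocol*

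**What the plan says.** Section 4.0 lists two hypoglycaemia measures among the secondary outcomes. Outcome 4 is "Change in percent Time hypoglycemic" (below 70 mg/dL) and outcome 5 is "Change in percent Time severely hypoglycemic" (below 54 mg/dL). Each runs from baseline to the 90-day and 180-day visits, and neither has a direction.

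Section 2.2 gives directions for A1C and the BOLUS score in hypotheses 1 to 8, for example "Use of COIN2DOSE will result in a lower rise in A1C compared to the controls". Hypotheses 9 to 12 concern feasibility, quality of life and usability. None mentions hypoglycaemia.

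Section 20.1 ends with the only significance rule in that section. It is one-sided, is printed with a threshold of 0.5, and neither states a tail nor sets any outcome apart.

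The nearest thing to a general direction is in section 3.2, where one objective is to learn whether the interventions "show a preliminary trend for improvement in the outcomes of interest".

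Section 20.2, on the primary outcome only, works from a different basis: "Using an F-test and significant level (alpha) of 0.025".

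**The concern.** A one-sided test is defensible when only one direction is of interest and that direction is fixed in advance. For A1C and BOLUS the protocol does fix it. For time below 70 and below 54 mg/dL it does not, and either direction matters.

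- **An increase is plausible.** Sections 5.0 and 15.0 describe payments for mealtime boluses, or deductions for missed ones. More mealtime dosing could lower glucose too far. This is an inference; the protocol does not say it, and section 17.0 does not list hypoglycaemia as a risk.
- **A decrease is plausible.** Section 3.1 names severe hypoglycaemic events among the consequences of poor adherence.

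At stake is how the pilot reports a by-arm shift in hypoglycaemia. In the section 10.0 schedule, CGM is the only procedure that measures it quantitatively, and sections 2.1 and 3.2 say the results will inform a definitive trial.

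**Working it through.** This point turns on a decision rule. The protocol gives no computed figure for the hypoglycaemia outcomes, so there is nothing to reproduce first. The 74% power in section 20.2 belongs to the primary outcome and is not an input here.

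**Step 1. The rule against the outcomes**

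| Item | Direction stated? | Where |
|---|---|---|
| A1C, BOLUS | Yes, benefit | 2.2, hypotheses 1–8 |
| Time <70, time <54 mg/dL | No | 4.0, outcomes 4 and 5 |
| Significance rule | One-sided, tail not named, no exception | 20.1 |

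Three readings are open for outcomes 4 and 5:
- Tail toward a decrease (improvement, as section 3.2 suggests): the rejection region holds only decreases, so the probability of declaring an increase is 0 at any alpha, sample size or true effect.
- Tail toward an increase: harm can be declared, but no passage says this is meant.
- Tail not fixed: it could be picked after the data are seen. Taking whichever side looks better at 0.05 gives a real error rate of 2 × 0.05 = 0.10.

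**Step 2. Inputs for the illustration**
- Size: "Target sample size is 36 adolescents. The maximum number of subjects enrolled will be 72". At 1:1:1 (section 11.0), 36/3 = 12 and 72/3 = 24 per arm. The 20 per arm of section 20.2 lies between.
- Alpha: 0.05, an assumption. Section 20.1 prints 0.5 and section 20.2 uses 0.025.
- True increase versus control: d = 0.5, 0.8 and 1.0 SD. These are assumptions, because the protocol gives no SD or expected change for either outcome.
- Test: two-sample t, one active arm against control, all participants analysable. This simplifies the regression models of section 20.1.

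**Step 3. Formula**

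Degrees of freedom = 2n − 2; noncentrality = d × √(n/2). Power to flag the increase = P(T > t₀.₉₇₅), with T noncentral t.

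At n = 12: df = 22, t₀.₉₇₅ = 2.074, √6 = 2.449, so the noncentralities are 1.225, 1.960 and 2.449.

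**Step 4. Probability of declaring a true increase**

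| n per arm | d (SD) | One-sided, toward decrease | Two-sided 0.05 | One-sided 0.05, toward increase |
|---|---|---|---|---|
| 12 | 0.5 | 0% | 21.5% | 32.4% |
| 12 | 0.8 | 0% | 46.6% | 60.0% |
| 12 | 1.0 | 0% | 64.9% | 76.7% |
| 20 | 0.5 | 0% | 33.8% | 46.3% |
| 20 | 0.8 | 0% | 69.3% | 79.9% |
| 24 | 0.5 | 0% | 39.6% | 52.5% |
| 24 | 0.8 | 0% | 77.4% | 86.1% |

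**Step 5. What an interval would show**

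Half-width of the two-sided 95% interval, in SD units = t₀.₉₇₅ × √(2/n):
- n = 12: 2.074 × 0.408 = 0.85
- n = 20: 2.024 × 0.316 = 0.64
- n = 24: 2.013 × 0.289 = 0.58

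The intervals are wide, but they show how large an increase the data leave open, which a p-value toward a decrease does not.

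**The case against.** The strongest case against has five parts.

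1. **No tail is stated.** A reader might infer that an increase in hypoglycaemia could never be declared. The documents do not support that without a condition. Section 20.1 names no direction, and a one-sided test toward an increase would detect harm. The statement holds only if the tail is improvement. That is the natural reading of section 3.2, but still a reading.

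2. **The rule may not reach the secondary outcomes.** It closes a section whose models are described for the primary outcome, and a separate analysis plan may set out the CGM analyses. The first part is fair. But the rule is stated without limit, and the point rests on what it states, not on missing detail. The F-test in section 20.2 has no direction, but it concerns the primary outcome and does not exempt outcomes 4 and 5.

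3. **The harm mechanism is inferred.** This is right. Section 5.0 pays per mealtime window with at least one qualifying bolus, so extra boluses within a window earn nothing, and section 3.1 links severe hypoglycaemia to poor adherence. That leaves the direction uncertain, which is itself an argument against a one-sided test.

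4. **Safety is watched elsewhere.** A reader might infer that harm would pass without a flag. Section 21.0 does not support that: a data safety and monitoring board is to meet every 6 months and review participant safety and adverse events, whatever any p-value. Nothing prevents reporting estimated changes either. But section 21.0 specifies no by-arm comparison of CGM time below range.

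5. **A two-sided test is weak too.** At 12 per arm it misses a 0.5 SD increase in about 78% of trials (100 − 21.5). This stands, and is why the interval matters more than the test.

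**Conclusion.** The point holds in conditional form. Section 20.1 applies a one-sided rule, with no direction and no exception, to two outcomes for which the protocol gives no directional hypothesis and for which a shift either way is plausible. If the tail is improvement, an increase in hypoglycaemia cannot be declared significant; that zero follows from the rule and needs no assumption about SD, alpha or sample size. If the tail is open, it could be chosen after the data are seen.

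The comparison figures for a two-sided test, about 22%, 47% and 65% at 12 per arm, are illustrative. They rest on assumed increases of 0.5, 0.8 and 1.0 SD, alpha 0.05, a pairwise t-test and complete data.

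The point does not touch the A1C hypotheses, and it does not show that the interventions cause hypoglycaemia or that safety goes unmonitored. It is worth correcting because the pilot is meant to inform a larger trial. The printed threshold of 0.5 and its disagreement with the 0.025 of section 20.2 also need reconciling, but that concerns the size of alpha, not the direction of the test.

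**What to change.** In section 20.1, add one sentence with two parts: any one-sided test is confined to the A1C and BOLUS hypotheses of section 2.2, in the direction stated there; and secondary outcomes 4 and 5 are reported as arm-minus-control differences, for each active arm, with two-sided 95% confidence intervals.

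The change needs no extra data, visits or participants. Its price is some power to show a reduction in hypoglycaemia. By symmetry with the table, at 12 per arm and alpha 0.05, moving from a one-sided test toward a decrease to a two-sided test lowers that power from 32.4% to 21.5% at 0.5 SD, from 60.0% to 46.6% at 0.8 SD, and from 76.7% to 64.9% at 1.0 SD, about 11 to 13 points. Since the protocol states no hypothesis of a reduction, little is given up.
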